7.2.2 Epoetin Alfa Treatment

7.2.2.1 Epoetin Alfa Administration and Schedule

Epoetin alfa (EPREX[®]/ERYPO[®] or PROCRIT[®]) will be administered as a subcutaneous injection once every week (7 days; QW) at a starting dose of 450 IU/kg (maximum total starting dose is 40,000 IU). Doses may be titrated up starting at dosing visit W7D1 (ie, Dose 7) as described in [Section 7.2.2.2](#). Individual epoetin alfa doses according to body weight will be rounded: up to the next 2,000 IU dose level for Starting Dose Level and Dose Level -1; and up to the next 4,000 IU for Dose Level +1 and Dose Level +2 for doses exceeding a calculated dosing of 56,000 IU according to body weight (maximum total dose is 80,000 IU).

As epoetin alfa is dosed according to body weight, subject weight will be assessed at every third epoetin alfa dosing visit (ie, W1D1, W4D1, W7D1, etc.) and in the event of a dose delay at restart of treatment. Changes of body weight of $\leq \pm 5\%$ do not require a dose adjustment.

Epoetin alfa will be administered as a subcutaneous injection by the site staff. Starting with the W7D1 Visit, site visits for IP administration are only required every third dose (ie, W10D1, W13D1, W16D1, etc.) and self-administration or administration by a nursing service is permitted between dosing site visits at the discretion of the investigator (ie, W8D1 and W9D1; W11D1 and W12D1, etc.) if in line with local practice. In the event dose adjustments of epoetin alfa are required, dosing should occur at the clinical site only until the dose adjustment process has been completed.

Administration of IP will be documented in the subject's source record. Compliance of self-administration of epoetin alfa will be monitored via the use of a medication diary card or other local procedures in place at the investigational site.

Subjects must have hemoglobin and blood pressure assessed prior to each IP administration when administered at the clinical site.

In addition, the clinical site staff must also confirm (and document in the subject's source record) if any transfusions were received by the subject (including any transfusions received at institutions outside of the study site in between study visits) prior to each IP administration. In addition to local procedures in place at the site to capture this information, a patient transfusion diary will be provided to subjects and will be reviewed by the site when/if returned by the patient.

7.2.2.2 Epoetin Alfa Dose Adjustment and Modification

Appropriate dose adjustments should be made to maintain hemoglobin concentrations within the target range of 10 g/dL to 12 g/dL (6.2 mmol/L to 7.5 mmol/L) independent of transfusions. Starting as soon as the W7D1 dosing visit (ie, Dose 7) of epoetin alfa and assessed by the investigator, subjects may have the dose level increased in a stepwise manner beyond the starting dose of 450 IU/kg to 787.5 IU/kg and 1,050 IU/kg (total dose 80,000 IU). Dose increases and decreases should be done one dosing level at a time (Table 6). A minimum of 4 weeks should elapse between dose increases.

Dose delay and/or reduction or discontinuation may be required due to increased Hgb or adverse events. For details on dose modification guidance for epoetin alfa please refer to Table 7.

Table 6: Epoetin Alfa Starting Dose Level with Dose Reductions and Dose Titration

Dose Level -1	Starting Dose Level	Dose Level +1	Dose Level +2
337.5 IU/kg (maximum total dose 40,000 IU)	450 IU/kg (maximum total dose 40,000 IU)	787.5 IU/kg (maximum total dose 80,000 IU)	1,050 IU/kg (maximum total dose 80,000 IU)

Individual epoetin alfa doses according to body weight will be rounded: up to the next 2,000 IU dose level for Starting Dose Level and Dose Level -1; and up to the next 4,000 IU for Dose Level +1 and Dose Level +2 for doses exceeding a calculated dosing of 56,000 IU according to body weight.

Table 7: Epoetin Alfa Dose Modification: Dose Delay, Dose Reduction, and Discontinuation Guidelines

Event at the Day of Dosing (Assessed prior to each IP administration at the respective visit ^k)	Action
Any suspected related AE \geq Grade 3 ^{a,b}	Dose delay ^c until resolved to \leq Grade 1 or baseline, and then reduce dose by one dose level according to Table 6.
> 2 dose reductions due to suspected related AE ^a	Discontinue treatment.
Δ Hgb > 2.0 g/dL (1.2 mmol/L) over 4 weeks (not influenced by RBC transfusions ^d)	Consider dose decrease by one dose level according to Table 6.
Predose Hgb ≥ 12.0 g/dL (7.5 mmol/L)	Dose delay until Hgb < 11.0 g/dL (6.8 mmol/L) ^d . Restart on same dose level or reduce by one dose level according to Table 6 (investigator judgement).
Loss of response or Hgb drop ≥ 1 g/dL (0.6 mmol/L) upon dose reduction	Increase by one dose level according to Table 6. A minimum of 4 weeks should elapse between dose increases.
$\geq 50\%$ increase in white blood cell count (WBC) compared to pre-dose WBC of previous treatment cycle and above upper limit of normal in the absence of an associated condition (eg, infection or concomitant corticosteroid use) ⁱ	Dose delay; recheck complete blood count (CBC), including WBC, at least weekly during dose delay. Treatment may be resumed if: WBC values below upper limit of normal ^e within 2 weeks

Table 7: Epoetin Alfa Dose Modification: Dose Delay, Dose Reduction, and Discontinuation Guidelines

Event at the Day of Dosing (Assessed prior to each IP administration at the respective visit ^k)	Action
	
If WBC remains above upper limit of normal^e for ≥ 2 consecutive weeks in absence of an associated condition (eg, infection or concomitant corticosteroid use); continue dose delay and collect bone marrow/peripheral blood samples to assess MDS disease status.
 
Treatment may be resumed if:
 
Absence of disease progression per IWG response criteria for altering natural history of MDS (Cheson, 2006)
 
AND
 
WBC values return below upper limit of normal
 
Discontinue treatment if:
 
Disease progression per IWG response criteria for altering natural history of MDS (Cheson, 2006)
 
OR
 
WBC remain above upper limit of normal^e

Presence of $\geq 1\%$ blasts in peripheral blood ⁱ (based on either local or central laboratory hematology sample)	
Dose interruption; immediately prepare peripheral blood smear^{f,g} for cytomorphology assessment by central pathology laboratory.
 
 • If central pathology laboratory cytomorphology assessment confirms $\geq 1\%$ blasts in the peripheral blood; discontinue treatment^h • If central pathology laboratory cytomorphology assessment determines $< 1\%$ peripheral blasts are present, repeat hematology assessment. 
 – If presence of $< 1\%$ blasts in peripheral blood, treatment can be resumed at next scheduled epoetin alfa administration. – If presence of $\geq 1\%$ blasts in peripheral blood; discontinue treatment^h

Abbreviations: AE = adverse event; CBC = complete blood count; Hgb = hemoglobin; IP = investigational product; IWG = International Working Group; MDS = myelodysplastic syndromes; RBC = red blood cell; WBC = white blood cell count.

^a Possibly, probably or definitely related to IP.

^b Includes systolic blood pressure ≥ 160 mmHg and diastolic blood pressure ≥ 100 mmHg.

^c If dose delay is > 12 consecutive weeks, treatment should be discontinued.

^d Predose Hgb value not being influenced by RBC transfusion (ie, Hgb result > 14 days after last RBC transfusion or within 3 days from next RBC transfusion); Hgb should be rechecked weekly during dose delay.

^e Upper limit of normal $> 10,000$ total WBC/ μ L or as defined by institutional standards.

^f Peripheral blood smear should be prepared for central pathology lab assessment.

^g At the investigator's discretion, bone marrow samples may also be collected and analyzed centrally to assess MDS disease status (eg, cytomorphology) prior to making decision regarding treatment discontinuation. The central laboratory must also confirm < 5% bone marrow blasts prior to resumption of treatment.

^h The investigator may contact the Medical Monitor prior to making decision regarding treatment discontinuation.

ⁱ Mandatory assessment only at 3-weekly visits (W4D1, W7D1, W10D1, etc.)

^k Every attempt should be taken to assess the blasts count in peripheral blood prior to dosing, however, in circumstances where results are not readily available at the time of planned dosing, the investigator may proceed with dosing provided there are no signs of clinical progression. In this case, results must be evaluated as soon as they become available (but no later than 3 days post dosing). If presence of $\geq 1\%$ blasts in peripheral blood is observed, actions described in table above must be followed immediately.

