7.2.1.2 Luspatercept Dose Adjustment and Dose Modification

Appropriate dose adjustments should be made to maintain hemoglobin concentrations within the target range of 10 g/dL to 12 g/dL (6.2 mmol/L to 7.5 mmol/L) independent of transfusions. Starting as soon as with dosing visit W7D1 (ie, Dose 3) of luspatercept, and assessed by the investigator prior to every subsequent luspatercept dosing, subjects may have the dose level increased in a stepwise manner beyond the starting dose of 1.0 mg/kg to 1.33 mg/kg, and up to a maximum of 1.75 mg/kg (Table 4), if all of the following criteria are met:

- Subject Hgb levels are below the target range of 10 g/dL to 12 g/dL (6.2 mmol/L to 7.5 mmol/L). If the Hgb levels are within 10 g/dL to 12 g/dL (6.2 mmol/L to 7.5 mmol/L) due to the influence of transfusions, the dose may still be adjusted (please consider the other three criteria noted below).
- Subject Hgb level increase compared to the Hgb sample taken prior to the previous luspatercept dose is ≤ 1 g/dL (0.6 mmol/L). If the Hgb level increase is > 1 g/dL due to the influence of transfusions, the dose may still be adjusted.
- The two most recent prior luspatercept administrations assessed must be at the same dose level.
- Subject must not have met protocol dose delay and/or reduction criteria in the two most recent luspatercept administrations (exception of dose delay required due to influence of RBC transfusions). Refer to Table 5.

If all criteria above are met, the dose may be increased by 1 dose level. The dose level should be titrated individually for each subject and must not exceed 1.75 mg/kg. Starting dose with dose increases and reductions are presented below for reference (Table 4).

Dose delay and/or reduction or discontinuation may be required due to increased hemoglobin or adverse events. For details on dose modification guidance for luspatercept please refer to Table 5.

Table 4: Luspatercept Starting Dose Level with Dose Reductions and Dose Titration

3rd Dose Reduction	2nd Dose Reduction	1st Dose Reduction	Starting Dose Level	1st Dose Titration Increase	2nd Dose Titration Increase
0.45 mg/kg	0.6 mg/kg	0.8 mg/kg	1.0 mg/kg	1.33 mg/kg	1.75 mg/kg

Table 5: Luspatercept Dose Modification: Dose Delay, Dose Reduction, and Discontinuation Guidelines

Event at the Day of Dosing (Assessed prior to each IP administration at the respective visit ^k)	Action

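### Epoetin Tables 6 and 7 conflict for some subjects: a mandatory reduction can point to a level that does not exist, or leave the dose unchanged in heavier subjects

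*Combined protocol and SAP*

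**What the plan says.** Section 7.2.2.2 governs epoetin dosing through two tables.

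- **Table 7, adverse event row.** After any suspected related event of Grade 3 or higher, dosing is held until the event resolves, "and then reduce dose by one dose level according to Table 6". No exception is made for a subject already at the bottom of the ladder.
- **Table 7, stopping row.** Treatment ends after more than two "dose reductions due to suspected related AE".
- **Table 7, hemoglobin rows.** These are discretionary. For a rapid rise the action is "Consider dose decrease by one dose level according to Table 6"; for a high predose value, restarting at the same or the next lower level is left to the investigator.
- **Table 7, loss-of-response row.** The dose goes up one level if response is lost, or hemoglobin falls, after a reduction.
- **Table 6.** There are four levels: Level -1 is "337.5 IU/kg (maximum total dose 40,000 IU", the start is "450 IU/kg (maximum total dose 40,000 IU", Level +1 is "787.5 IU/kg (maximum total dose 80,000 IU" and Level +2 is "1,050 IU/kg (maximum total dose 80,000 IU". Doses are rounded up, to 2,000 IU steps at the two lower levels and to 4,000 IU steps at the two upper levels once the calculated dose passes 56,000 IU.

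For luspatercept (Section 7.2.1.2), Table 4 lists three levels below the 1.0 mg/kg start: 0.8, 0.6 and 0.45 mg/kg. Table 5 has the same adverse event and stopping rows, but its row for a rapid hemoglobin rise makes the reduction mandatory.

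**The concern.** The stopping row presupposes that two adverse event reductions can be made before treatment ends. The epoetin ladder offers one step below the start. Up-titration cannot begin before W7D1, so until then every subject is at the starting level or Level -1.

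The upper and lower pairs of levels also share caps, so two levels with different names can deliver the same number of units.

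In either case a safety instruction for the control arm of an open-label trial cannot be followed as written, or has no effect when it is followed. The site must then choose between holding the dose and stopping. That choice can reach the results. Section 9.7.2 counts a subject discontinued before the end of Week 24 as a non-responder for RBC-TI for 24 weeks, and one discontinued without HI-E as an HI-E non-responder. Both endpoints are in the gated sequence. Section 7.3 also requires sites to record the new level in the IRT at any reduction, and here there may be none to record.

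**Working it through.** The plan gives no figure on this point to reproduce. The check is a count of levels, followed by arithmetic on Table 6.

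**1. Nominal steps down.** From Level -1: 0. From the start: 1. From +1: 2. From +2: 3. The stopping row requires more than 2 adverse event reductions.

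**2. Trace from the starting level.** The first qualifying event takes the subject to Level -1 (count 1). With no re-escalation, a second qualifying event orders a further reduction, and Table 6 has no entry below Level -1. Even if the undeliverable reduction is counted, the total is 2, which is not more than 2. So neither the reduction nor the stop applies, and no row or footnote covers the case. A discretionary hemoglobin reduction can use up the single step earlier, so that the first adverse event meets the same gap.

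**3. Delivered dose.** For weight w in kg:

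dose = min(cap, IU/kg × w rounded up to the step)

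- Level -1 reaches its cap once 337.5 × w exceeds 38,000, because the next 2,000 IU step is 40,000: w > 38,000/337.5 = 112.6 kg. The starting dose is already capped there (450 × 112.6 = 50,670 IU), so the two levels are equal.
- Level +1 reaches its cap once 787.5 × w exceeds 76,000, because the next 4,000 IU step is 80,000: w > 76,000/787.5 = 96.5 kg. Level +2 is already capped there (1,050 × 96.5 = 101,325 IU), so the two levels are equal.
- Without rounding, the thresholds would be 40,000/337.5 = 118.5 kg and 80,000/787.5 = 101.6 kg. Rounding is part of the rule, so the lower figures apply.
- The start and Level +1 did not coincide at any weight on a 40 to 140 kg grid.

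| Weight | -1 (IU) | Start (IU) | +1 (IU) | +2 (IU) | Reductions that lower the dose, from Start / +1 / +2 |
|---|---|---|---|---|---|
| 70 kg | 24,000 | 32,000 | 56,000 | 76,000 | 1 / 2 / 3 |
| 100 kg | 34,000 | 40,000 | 80,000 | 80,000 | 1 / 2 / 2 |
| 113 kg | 40,000 | 40,000 | 80,000 | 80,000 | 0 / 1 / 1 |

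No rounding step is stated for +1 and +2 at or below 56,000 IU. I assumed 2,000 IU, which affects only the +1 entry at 70 kg and neither threshold.

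**4. Luspatercept.** Adverse events alone from the start give 1.0 to 0.8 to 0.6 to 0.45 mg/kg. The third such reduction meets the stopping row before the ladder is exhausted. Now take two mandatory hemoglobin reductions (to 0.6) and one adverse event reduction (to 0.45). The next qualifying adverse event has no lower level, and the adverse event count is 1, or 2 if the undeliverable reduction is counted. The same kind of gap appears, but after more events.

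**The case against.** The best defence has four parts.

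- **The tables are guidance.** Both are titled as guidelines. Dosing is held until the event resolves, and a delay of more than 12 consecutive weeks ends treatment.
- **Clinicians have a way out.** Section 11.1 makes an adverse event sufficient reason to stop, leaves the decision to the treating physician and allows contact with the Medical Monitor.
- **The ladder is often long enough.** A subject at +2 has three steps down. One at +1 has two, and a third event can be read as meeting the stopping row.
- **The stopping rule can be reached.** Table 7 counts reductions and does not require an unbroken descent. A subject who goes from the start to Level -1, back up under the loss-of-response row, and down again can accumulate three.

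All four stand as limits on scope, and the second limits harm. None says what Table 7 requires when no lower level, or no lower actual dose, remains. Footnote h, which mentions the Medical Monitor, is attached only to the blast row.

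A reader might infer that the epoetin stopping rule can never be met. The fourth part shows that this goes too far.

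A reader might also infer that only the control arm is affected. The mandatory hemoglobin reductions in Table 5 show otherwise, so a one-sided distortion between arms is not established.

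**Conclusion.** The conflict is real, and the tables are wrong as written rather than merely short of detail. It has two forms:

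- an epoetin subject reduced from the starting level to Level -1, not re-escalated, who has another qualifying event;
- a subject above about 112.6 kg at the starting level, or above about 96.5 kg at +2, for whom the ordered reduction leaves the dose unchanged.

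It would be wrong to conclude that every subject above 112.6 kg is affected at the first event. At +1, such a subject steps from 80,000 to 40,000 IU.

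The documents give neither a weight distribution nor event counts, so the share affected is unknown, and no effect on any estimate can be quantified. Alpha, power and sample size are unaffected. The thresholds rest on the caps and rounding steps as printed. The point should be corrected because it concerns a safety instruction and the correction is cheap.

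**What to change.** Reconcile Table 6 (levels, caps and rounding) with Table 7, and check Table 4 against Table 5. Each ordered action should be possible from each dose level and body weight, and should fit the discontinuation rule. State explicitly what applies when no lower level, or no lower actual dose, is available, and how such an event counts toward stopping. State the rounding step for the two upper epoetin levels at or below 56,000 IU. Align the IRT with the result. Which levels and which rule to adopt is for the clinical team; no dose or stopping rule is proposed here.

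The cost is table wording in the next amendment and an IRT check.

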7.2.3 Overdose

7.2.3.1 Luspatercept Overdose

On a per dose basis, an overdose for luspatercept is defined as the following amount over the protocol-specified dose of luspatercept assigned to a given subject, regardless of any associated adverse events or sequelae.

Subcutaneous injection 10% over the protocol-specified dose

On a schedule or frequency basis, an overdose is defined as anything more frequent than the protocol required schedule or frequency. Complete data about drug administration, including any overdose, regardless of whether the overdose was accidental or intentional, should be reported in the eCRF. See [Section 10.1](#) for the reporting of adverse events associated with overdose.

7.2.3.2 Epoetin Alfa Overdose

On a per dose basis, an overdose for epoetin alfa is defined as the following amount over the protocol-specified dose (applying the rounding rules as specified in [Section 7.2.2.1](#)) of epoetin alfa assigned to a given subject, regardless of any associated adverse events or sequelae.

Subcutaneous injection 10% over the protocol-specified dose

On a schedule or frequency basis, an overdose is defined as anything more frequent than the protocol required schedule or frequency. Complete data about drug administration, including any overdose, regardless of whether the overdose was accidental or intentional, should be reported in the eCRF. See [Section 10.1](#) for the reporting of adverse events associated with overdose.

7.3 Method of Treatment Assignment

The treatment assignment (randomization) will occur at the end of the Screening Period, once all required screening procedures have been completed and all inclusion and exclusion criteria have been assessed to determine eligibility of the subject. Subjects deemed eligible for the study will be randomized by a central randomization procedure using IRT.

Designated research personnel at each investigational site will be assigned password protected, coded identification numbers which gives them the authorization to call into IRT to randomize subjects.

For drug assignment at dosing visits and in the event of any dose reduction or dose titration site staff must contact IRT to record the new dose level and obtain the new IP assignment.

The relationship of the randomization number to the subject identification (ID) number will be described by a randomization algorithm. The randomization algorithm will be employed by the IRT system to assign a subject to a treatment based on the prespecified rules, such as open-label study, stratified randomization with randomization ratio active versus comparator on a 1:1. Subjects will be placed into the appropriate stratum per the responses/data entered/collected for questions collecting stratification factors and based on the combination of these data points, the IRT will place the subject in the next available slot within the appropriate stratum for that subject. The IRT will be utilized to ensure an equal weight central randomization based on randomization method according to stratification factors defined in [Section 3.1](#). The randomization number corresponds to a particular treatment arm within a stratum.

7.4 Packaging and Labeling

Where centrally supplied, the label(s) for IP will include sponsor name, address and telephone number, the protocol number, IP name, dosage form and strength (where applicable), amount of IP per container, lot number, expiry date (where applicable), medication identification/kit number, dosing instructions, storage conditions, and required caution statements and/or regulatory statements as applicable. Additional information may be included on the label as applicable per local regulations.

7.5 Investigational Product Accountability and Disposal

7.5.1 Accountability Procedures

Accountability for IP that is administrated during the course of the study is the responsibility of the investigator or designee.

Investigational clinical supplies must be received by a designated person at the clinical site and kept in a secure and temperature-controlled location. The investigational site must maintain accurate records demonstrating dates and amounts of IP received, to whom it was administered (subject-by-subject accounting), and accounts of any IP accidentally or deliberately destroyed or returned.

Accurate recording of all IP administration will be made in the appropriate section of the subject's eCRF and source documents.

For luspatercept and epoetin alfa vials (PROCRIT[®] [US]), unless otherwise notified, all vials, both used and unused, should be saved for drug accountability purposes. The used vials may be discarded, per the institution's standard operating procedures, after drug accountability has been completed by the monitor. For epoetin alfa prefilled syringes (EPREX[®]/ERYPO[®] [ex-US]), only unused IP must be saved for drug accountability purposes as used syringes must be discarded in sharp containers, unless otherwise notified.

